11.4.4 EFFICACY

Treatment responses

Computer Tomography or MRI will be performed at Screening, prior to the start of Cycles 1 (only in the Dose Escalation cohorts if the previous scan was done more than 28 days previously), at the end of Cycles 2, 4, and 6, at 6, 9 and 12 months after the start of the combination therapy and at the End of Study (Month 18) or at Early Termination (ET) if the patient discontinues from the trial. Changes in the size and number of target lesions will be evaluated using RECIST v1.1 criteria, compared to baseline (Screening) or prior to Cycle 1 scan whichever is appropriate.

Other Outcome Measures

Each patient's ECOG Performance status will be assessed at the end of NOX66 monotherapy, at the start of Cycle 5 and at End of Study, compared to baseline. Assessments of pain, fatigue and QOL will be made at the end of NOX66 monotherapy (fatigue and pain only), on Day 1 of each cycle for the combination of NOX66 and doxorubicin, at Months 6, 9 and 12 of the follow-up period and at the End of Study, compared to baseline. Assessments of acceptance of suppository administration will be made at the end of NOX66 monotherapy and on Day 1 of each cycle for the combination of NOX66 and doxorubicin.

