	
Radiological Imaging
 
Tumor imaging (CT/MRI) for determination of response rate and PFS during the study, will be performed at Screening (if scans are not done within 28 days of registration and Cycle 1 Day 1), prior to the start of Cycles 1 (only in the Dose Escalation Cohorts if the baseline scan was done more than 28 days from C1D1), at the end of Cycles 2, 4 and 6, at 6, 9 and 12 months after the start of the combination therapy and at the End of Study or at Early Termination (ET) if the patient discontinues from the trial.

Safety Assessments

Adverse events (AEs) will be monitored by the Investigator during the study. Other safety assessments will include physical examination, vital signs, 12- lead ECGs (including Holter recordings), hematology, clinical chemistry, and urinalysis laboratory tests, as well as brain type natriuretic peptide (BNP) and troponin I assessments.

Study Period and Duration of Treatment	Screening will take up to 28 days prior to the first dose of NOX66. The study duration from initial administration of NOX66 to the last follow up is approximately 20 months including Screening. The lead-in NOX66 monotherapy period is 12 days, then 6 x 21-day cycles of NOX66 + doxorubicin, followed by 14 months of active follow up (including scheduled visits and telephone follow-up / chart review for PFS and OS).
Study Sites and Location	Approximately 12 sites in the United States and Australia

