10.2.3 DOSE MODIFICATIONS

The dose of doxorubicin can be reduced from 75 to 60 mg/m² if a Grade 2 toxicity related to doxorubicin occurs. If serum bilirubin is 1.2-3.0 mg/dL prior to a cycle, a 50% dose reduction of doxorubicin is recommended. If serum bilirubin is 3.1-5.0 mg/dL prior to a cycle, a 75% dose reduction of doxorubicin is recommended.

If a perineal and/or anal rash develops (Grade 1-2), a topical hydrocortisone containing haemorrhoid cream/ointment and/or cutaneous cream should be used. For Grade 3-4 perineal and/or anal rash, NOX66 treatment should be delayed until the rash resolves to Grade 1 or completely. NOX66 should also be delayed if there is proctitis, rectal mucositis, or ulcer of Grade 2 or higher. Treatment may be resumed when toxicity decreases to Grade 1. Treatment with NOX66 should also be delayed in the presence of anorectal infections and may be resumed after they are resolved.

All dose delays for NOX66 and doxorubicin need to be discussed with the Medical Monitor.

For patients developing neutropenia, the following guidelines should be used for doxorubicin dose modification.

Toxicity	Recommended Dose Modification
ANC < 1,000	No doxorubicin administered; treatment cycle delayed
≥ Grade 3 neutropenic fever/infection	Approximately 60 mg/m ² doxorubicin
≥ Grade 4 neutropenia lasting longer than 1 week	Approximately 60 mg/m ² doxorubicin
Second incidence of either: 1) ≥ Grade 3 neutropenic fever/infection 2) Grade 4 neutropenia lasting longer than 1 week	Second dose reduction to 45 mg/m ²
Reversible Grade 3 neutropenia with fever/infection or Grade 4 ANC	Retreatment with doxorubicin at Investigator's discretion

Abbreviation: ANC = absolute neutrophil count

In the event of cardiac toxicity (e.g., if there is an absolute decrease in LVEF of >10% from the previous evaluation, or if the actual LVEF decreases to ≤40%) doxorubicin must be discontinued. Doxorubicin must also be discontinued if the patient develops Grade 3 or 4 left ventricular systolic dysfunction (symptomatic congestive heart failure).

Patients who discontinue doxorubicin after 4 cycles of treatment should complete the remaining 2 cycles of NOX66 as planned. If doxorubicin is discontinued prior to 4 cycles, NOX66 treatment may continue in consultation and agreement with the Medical Monitor.

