11.2.2 TREATMENT DISCONTINUATION

Patients will be discontinued from the study treatment if any of the following occurs as noted in Section [9.5](#).

- Disease progression based on RECISTv1.1
- An inter-concurrent illness that prevents further administration of NOX66
- An adverse event that is intolerable to continue the treatment with NOX66 and doxorubicin or any DLT (Section [8.3](#)) that has not resolved to Grade 1.
- Any other reason the Investigator considered that impacts the patient's safety.

For the patients who discontinue treatment, they will continue on study for follow-up visits for tumor evaluation. All anti-cancer treatments should be recorded in the eCRF. In those patients who have evidence of disease progression during the combination of NOX66 and doxorubicin, additional tumor evaluation assessments are not needed.

If a patient is withdrawn from the study at any time, either at his/her request or at the Investigator's discretion, regardless of the reason, the Investigator will record on the relevant page of the eCRF the reason(s) for withdrawal and the day of last dosing. The eCRF (and the clinical study report) will include reasons for patient withdrawals, as well as other details relevant to the patient's withdrawal.

Any patient who appears to be noncompliant from Cycles 2 to 6 should be counselled but not withdrawn from the study. Patients who discontinue for non-safety related reasons or for noncompliance prior to the end of Cycle 1 in the Dose-Escalation Part can be replaced.

Should any patient withdraw or be withdrawn from the study prior to the completion of the Month 18 follow-up visit, every effort should be made to complete the assessments at the End of Study (Section [11.6.2.12](#)). Patients experiencing adverse events should be followed until the AE has resolved, stabilized, or is no longer deemed clinically significant, as judged by the Investigator. Appropriate supportive and/or definitive therapy will be administered as required.

Discontinuation due to treatment failure, as defined by disease progression, is to be expected since doxorubicin is not curative for sarcoma and the optimal dose and dose frequency is not known for NOX66. Alternate treatments for sarcoma may be offered to the patient.

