11. The additional tests for hematology and serum chemistry on Days 9 and 16 are to assess any hematological or clinical laboratory tests for DLTs and/or require a dose reduction to 60 mg/m^2 or lower (37.5 mg/m^2 or 18.75 mg/m^2 based on serum bilirubin), or a delay in initiation of another cycle of the combination. These additional hematological and clinical laboratory tests should be performed at each cycle. Visit windows are ± 2 days of the scheduled visit.
12. During combination treatment cycles, NOX66 is administered on Days 1 to 7 and doxorubicin is administered on Day 2.
13. Doxorubicin (75 mg/m^2 or reduced dose) to be given on Day 2 of each 21-day cycle.
14. For Dose-Escalation Cohorts, PK samples will be obtained at pre-dose and at 1 and 2 hours post NOX66 on Day 2 Cycle 1. PK samples for idronoxil will be obtained on Day 2 of Cycles 2, 4 and 6 at pre-dose and 4 hours post dose. Additional PK samples for idronoxil will also be obtained pre-dose on Day 7 and at 8 or 12 hours after the last dose of NOX66 on Day 7 for those on a TID or BID regimens, respectively on Cycles 1, 3, and 5. For the Dose Expansion Cohort, PK samples for idronoxil will be obtained on Day 2 of Cycles 1, 2, 4, and 6 at pre-dose and at 4 hours post NOX66 and on Cycle 1 at 6 hours post NOX66. On Cycles 1, 3, and 5 PK samples are to be collected just prior to the morning dose of NOX66 on Day 7. For doxorubicin in the Dose Escalation Cohort, PK samples will be obtained at 0.5, 4 and 6 hours after the end of infusion on Day 2 Cycle 1 and at 0.5 and 4 hours at the end of infusion on Day 2, Cycles 2, 4 and 6. For doxorubicin in the Dose Expansion Cohort, PK samples will be obtained at 0.5, 4 and 6 hours after the end of infusion on Day 2 Cycle 1 and at 0.5 and 4 hours at the end of infusion on Day 2, Cycles 2, 4 and 6 ([Table 7](#)).
15. All patients who discontinue the study early for whatever reason after the first dose of NOX66, or during treatment cycles (Cycles 1-6), will be followed up within 28 days of discontinuation and submit to assessments detailed in the column of Cycle 6 Day 21/Early Termination. Patients who discontinue the study early during the follow-up period will complete a final visit with assessments detailed in the column of End of Study/Early Termination. Patients who complete the study in full will have an End of Study visit at Month 18.
16. Adverse events to be recorded up to 30 days after the last dose of NOX66 or doxorubicin, whichever is longer.

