14.3.10 EFFICACY ANALYSES

Treatment response will be assessed by RECIST v1.1 criteria for patients in the FAS at the end of Cycles 2, 4, and 6, at the 6-month, 9-month, and 12-month follow-up visits, and at the End of Study or Early Termination. Along with CR, PR and SD, the ORR will be defined as the relative frequency of patients with either CR or PR, and the DCR will be defined as the relative frequency of patients with CR, PR, or SD.

The ORR, the DCR, and the frequencies of CR, PR, SD, and PD will be summarized at the end of Cycles 2, 4 and 6 and at the 6-month, 9-month, 12-month and up to 18-month follow-up visits. A summary will also be provided of best response on study.

At the assessment at the end of Cycle 6, a one-sided exact binomial test will be used to test the null hypothesis that the ORR is no greater than 0.20 (20%) against the alternative hypothesis that the ORR is greater than 0.20 at an approximate level $p = 0.025$. A similar test against the performance level of 0.20 will be performed for the rate of best objective response on study.

Overall survival will be defined as the time in months from initial treatment until death or censoring. Patients not known to have died at the time of analysis will be censored at the time of last contact with study personnel., including patients who are lost to follow-up. The overall survival curve will be estimated for the FAS by the Kaplan-Meier method.

Progression-free survival will be defined as the time in months from initial treatment until death, disease progression, or censoring. Patients who are lost to follow-up will be censored at the time of their last contact with study personnel. Patients who leave the study to begin an alternative therapy will be censored on their day of study discontinuation. The PFS curve will be estimated for the FAS by the Kaplan-Meier method.

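### Tumour scans follow cycle number and then calendar months, so a patient who stops all study treatment without progression misses the remaining 6-weekly scans and any progression is found late

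*Combined protocol and SAP*

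**What the plan says.** - **On treatment.** The synopsis plans "6 x 21-day cycles of NOX66 + doxorubicin". Sections 11.6.2.5, 11.6.2.7 and 11.6.2.9 put the scans on Day 21 of Cycles 2, 4 and 6, nominally Days 42, 84 and 126.
- **Later.** Section 11.4.4 continues with scans "at the end of Cycles 2, 4, and 6, at 6, 9 and 12 months after the start of the combination therapy" and then "at the End of Study (Month 18) or at Early Termination (ET) if the patient discontinues from the trial". Table 2 counts the follow-up months from Cycle 1 Day 1.
- **Cycle delay.** In 10.2.3, the consequence of a low neutrophil count is "No doxorubicin administered; treatment cycle delayed". No maximum delay is given, and no calendar date is set for the on-treatment scans.
- **Stopping treatment.** Section 11.2.2 states: "For the patients who discontinue treatment, they will continue on study for follow-up visits for tumor evaluation". The first such visit is Month 6. Patients who have already progressed on the combination need no further tumour assessment.
- **Early Termination (ET) visit.** Table 4 footnote 15 covers "All patients who discontinue the study early for whatever reason after the first dose of NOX66", who "will be followed up within 28 days of discontinuation and submit to assessments detailed in the column of Cycle 6 Day 21/Early Termination". That column includes CT/MRI.
- **Analysis.** Section 14.3.10 estimates PFS by Kaplan-Meier in the FAS, with no rule for late scans or interval censoring. For response it says "At the assessment at the end of Cycle 6, a one-sided exact binomial test will be used".

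**The concern.** Progression seen on imaging can only be dated at a scan. If the scan dates depend on staying in cycles, stopping treatment for toxicity changes when progression can be seen, apart from any effect on the tumour. Patients who stop early then tend to have later recorded progression dates.

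The study has no control arm, so its PFS will be read against historical figures or across dose levels. Both comparisons are affected if the share of patients stopping early differs. Early stoppers also have no scheduled scan at the end-of-Cycle-6 response assessment.

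**Working it through.** **1. The plan's own timeline.** 6 × 21 = 126 days; 126/30 = 4.2 months; 6 − 4.2 = 1.8 months; 4.2 + 1.8 + 4 × 3 = 18 months. This reproduces Table 2. With 30.44-day months, Month 6 is about Day 183.

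**2. Scan days for a patient who stops all treatment after a clear Day 42 scan.**

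| Case | Scan days up to Month 6 | Longest gap after Day 42 |
|---|---|---|
| Stays in cycles | 42, 84, 126, 183 | 57 days |
| Stops, no ET scan | 42, 183 | 183 − 42 = 141 days |
| Stops, ET scan at the 28-day limit | 42, 70, 183 | 183 − 70 = 113 days |

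**3. Does stopping treatment trigger the ET scan?** Sections 11.4.4 and 11.6.2.9 and Table 4 footnote 15 speak of leaving the trial or study. Section 11.2.2 keeps patients who stop treatment on study. Against that, the echocardiography sentence in the synopsis applies ET to patients who discontinue before 6 cycles, and Table 9 footnote b (pharmacodynamic samples) applies it to those who discontinue treatment before Cycle 6. Both readings are therefore carried forward.

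**4. Detection lag.** Assumption: exponential progression with the median PFS values cited in 6.1 (4.1, 4.6, 6.6 and 7.4 months). Let λ = ln 2 / median in days, and L = 141 days.

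- Share progressing before Day 183: 1 − exp(−λL).
- Mean lag among them with no ET scan: L / (1 − exp(−λL)) − 1/λ.
- Median 4.1 months: λ = 0.6931/124.8 = 0.00555; share 54%; lag 141/0.543 − 180 = about 80 days.
- Median 7.4 months: λ = 0.6931/225.3 = 0.00308; share 35%; lag 141/0.352 − 325 = about 76 days.

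Splitting the interval at the scan days gives 49 to 50 days with an ET scan at Day 70, and 24 days with scans at Days 84, 126 and 183.

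**5. Effect on mean PFS, restricted to 18 months.** Each progression is dated to the first scan on or after it and compared with the nominal schedule.

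| Scenario | Change in mean PFS, medians 7.4 to 4.1 months |
|---|---|
| Stop after Cycle 2, no ET scan | +0.52 to +0.78 months |
| Stop after Cycle 2, ET scan at Day 70 | +0.25 to +0.36 months |
| Every cycle delayed one week, no stop | +0.04 to +0.07 months |
| Every cycle delayed two weeks, no stop | +0.06 to +0.12 months |

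Whole group, if 20% stop after Cycle 2: 0.2 × 0.52 = 0.10 to 0.2 × 0.78 = 0.16 months without ET; 0.2 × 0.25 = 0.05 to 0.2 × 0.36 = 0.07 months with it. The 20% and the delay lengths are assumptions; the documents give neither.

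**6. Reported median.** It jumps between scan dates.

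- True median 4.1 months: the nominal curve at Day 126 is exp(−0.00555 × 126) = 0.497, so the median reads 4.14 months. If 10% stop after Cycle 2 without ET, their curve is still at exp(−0.00555 × 42) = 0.792, and the mixture is 0.9 × 0.497 + 0.1 × 0.792 = 0.526. The median then moves to 6.00 months.
- True median 4.6 months: a one-week delay in every cycle for all patients moves it from 6.00 to 5.29 months, which is shorter.
- True medians 6.6 and 7.4 months: it stays at 9.00 months with 10% to 30% stopping after Cycle 2.

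**The case against.** The strongest reply is that the ET scan closes much of the gap. Section 9.4 lists only withdrawn consent and death as study withdrawal, so an ET scan that needed study withdrawal would hardly ever be done; the authors may well have meant it for anyone stopping treatment. A reader might infer from 11.4.4 and 11.2.2 that such a patient certainly goes 141 days without imaging. The documents do not settle that. What stands is that 113 days remain even on the kinder reading.

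Other replies also have force:

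- **Stopping doxorubicin is not stopping treatment.** Under 10.2.3, patients who stop doxorubicin after 4 cycles should go on with NOX66, and earlier stoppers may. They stay in cycles and keep their scans. The point concerns only those who stop both drugs.
- **How many are affected is unknown.** Section 6.1 cites 3% and 18% of patients unable to complete six cycles because of adverse events. These refer to stopping at any time, and the 18% belongs to doxorubicin plus ifosfamide. They cannot be read as a forecast of stops after Cycle 2. A stop after the Cycle 4 scan without ET adds only 0.17 to 0.23 months (medians 7.4 to 4.6).
- **Response rates.** A reader might infer that the Cycle 6 rates describe only patients who tolerated treatment. Sections 11.1.2.2 and 14.3.10 keep all FAS patients in the denominator, and best response on study is tested as well. What remains is that early stoppers have no scheduled scan at that time point.
- **Role of PFS.** It is secondary and descriptive, with no test and no between-arm contrast to bias.

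**Conclusion.** The concern holds in a limited form. Stopping all treatment without progression removes the remaining 6-weekly scans and leaves 113 or 141 days without imaging after an early stop, so detection is two to three times as slow as under continued scanning. Mean PFS rises by about 0.25 to 0.78 months for a patient stopping after Cycle 2, and by about 0.05 to 0.16 months for the group at an assumed 20% share.

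The broader reading, that toxicity in general lengthens the reported PFS, is not supported. Cycle delays alone add about 0.1 month or less, because Month 6 is fixed from Cycle 1 Day 1, and the reported median can move either way.

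The figures assume exponential progression and ignore deaths and clinical progression between scans. They also leave out the 12 days by which PFS starts before Cycle 1 Day 1 in the escalation cohorts. Patients who stop before completing Cycle 1 are outside the FAS and do not enter PFS.

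**What to change.** This is a cheap improvement in protocol wording.

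1. In the synopsis imaging paragraph, 11.4.4, 11.6.2 and Table 4 footnote 2, schedule CT/MRI at Weeks 6, 12 and 18 and then Months 6, 9, 12 and 18 from Cycle 1 Day 1, until progression and regardless of cycle delay or treatment stop. The treatment-dependent shift then vanishes by construction, and the longest gap before Month 6 is 183 − 126 = 57 days.
2. Use the Week 18 scan for the end-of-Cycle-6 ORR in 14.3.10.
3. Reconcile 11.4.4, 11.6.2.9, Table 4 footnote 15, the synopsis echocardiography sentence and Table 9 footnote b on whether stopping treatment triggers the ET visit and its scan.

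Cost: early stoppers have the Week 12 and 18 scans off treatment, which they would not have now, but within the number already planned per patient. A delayed patient's scan may fall mid-cycle, so the footnote 2 wording that links the next cycle to the scheduled scan has to be reconciled with the new dates.

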11.4.5 PHARMACODYNAMICS

Changes from baseline in blood/plasma levels of cytokines, chemokines, lipids and ENOX2 will be assessed on Day 7 of Monotherapy, at the beginning of Cycle 3 and at end of Cycle 6.

11.5 ASSESSMENT OF DISEASE STATUS

11.5.1 RADIOLOGIC

Computer tomography or MRI will be used to assess the size and number of all measurable target and non-target lesions as defined in RECIST v1.1. For each patient, the same modality must be used at baseline and throughout the study.

11.5.2 TREATMENT RESPONSE

Assessment of treatment response: Treatment response will be separately assessed at the end of Cycles 2, 4, and 6 and End of Study compared to baseline. The RECIST v 1.1 criteria will be used to evaluate tumor responses to determine 1) Disease Control Rate (DCR) defined as [(stable disease (SD) + partial response (PR) + complete response (CR)/All)], b) overall response rate (ORR)(PR+CR)/All), c) OS and d) PFS.

All radiologic images will be reviewed by an independent, experienced, local radiologist to assess RECIST response. The same radiologist should review each patient's scan.

11.6 STUDY VISITS

The study activities and procedures are summarized in [Table 4](#). Details of study procedures are provided in this section. A visit schedule for the period projected from the date of first dose of study drug to the date of the final Treatment Period Visit should be established for each patient by study site staff.

11.6.1 SCREENING (DAYS -28 TO -1)

Study screening will occur approximately 2 to 28 days before Day 1. For the purposes of this study, patients will be considered enrolled when they provide signed informed consent and have met eligibility criteria. Written informed consent will be provided before any study-related procedures are performed. At screening, patients will be assigned a patient identification number and then all patients will be identified by their unique study patient number throughout the study.

The following will take place at Screening:

- Obtain informed consent by the patient prior to any study-related procedures.
- Assign patient identification number.
- Record demographics.
- Record medical/surgical history.
- Record histopathology and grade of STS.

- Obtain archival tissue samples (or 10 unstained histology slides), if available (optional). This can be collected any time during the study.
- Record prior and concomitant medications.
- Measure vital signs (blood pressure, pulse [radial or brachial (to be measured over 30 seconds if performed manually)], respiration rate and oral body temperature.
- Perform a physical examination, including body weight and height.
- Record ECOG performance status.
- Obtain a 12-lead ECG (Section [11.4.2.3](#)).
- Perform echocardiography (Section [11.4.2.3](#)).
- Collect urine and fasting blood samples for clinical laboratory tests (hematology, serum chemistry and urinalysis, Section [11.4.2.3](#)). Calculate creatinine clearance using Cockcroft-Gault equation.
- Females of childbearing potential will undergo a urine pregnancy test (per inclusion criteria [Section [9.2](#)], negative results must be obtained prior to dosing with study drug).
- Assess inclusion/exclusion criteria (Sections [9.2 and 9.3](#)).
- Document all measurable tumor lesions with CT or MRI. If scans are available within 28 days of the first dose of NOX66 (Dose-Escalation Phase) or before Cycle 1 in Dose-Expansion Cohort there is no need for additional scans.
- Assess AEs and update medical history (Section [15.2.1](#)).
- Patients must indicate willingness to self-administer study drug rectally. Instructions will be provided and competency in self-administration of a suppository similar in size to NOX66 must be demonstrated at the study site. Alternatively, if a given patient is accompanied by a reliable and willing household member, that individual may be trained to administer study drug to the patient and will be required to demonstrate competency at the study site.

Results of these screening evaluations will be used to determine the patient's eligibility to receive study drug according to the inclusion and exclusion criteria (Sections [9.2 and 9.3](#), respectively). Eligible patients who are selected and wish to continue will be scheduled to return for baseline (Day 1) assessments.

Patients who have given their informed consent, have completed all baseline evaluations, and have met all inclusion and no exclusion criteria (reconfirmed at baseline) will self-administer a single dose of NOX66 rectally.

